7.3 Sample Collection and Handling

The actual dates and times of sample collection must be recorded in source documents for transcription to the eCRF or laboratory requisition form. Refer to the Schedule of Assessments (Appendix 1 and Appendix 2) for the timing and frequency of all sample collections.

Instructions for the collection, handling, and shipment of samples are found in the Laboratory Manual.

8. STUDY PROCEDURES

Before study entry, throughout the study, and following study drug discontinuation, various clinical and diagnostic laboratory evaluations are outlined. The purpose of obtaining these detailed measurements is to ensure adequate safety and tolerability assessments. Clinical evaluations and laboratory studies may be repeated more frequently if clinically indicated. The Schedules of Assessments for Phase 1b and Phase 2 are provided in Appendix 1 with PK, pharmacodynamics, and biomarker collection details in Appendix 2.

8.1 Screening Phase

Screening procedures will be performed up to 28 days before Day 1, unless otherwise specified. All subjects must first read, understand, and sign the IRB/REB/IEC-approved ICF before any study-specific screening procedures are performed. After signing the ICF, completing all screening procedures, and being deemed eligible for entry, subjects will be enrolled in the study. Procedures that are performed prior to the signing of the ICF and are considered standard of care may be used as screening assessments if they fall within the 28-day screening window. The pretreatment tumor tissue biopsy may be within 3 months.

8.1.1 Screening/Consenting Visit

The following procedures will be performed during Screening:

- Informed Consent
- Review of eligibility criteria (Inclusion/Exclusion criteria)
- Medical history and demographics
- Complete physical exam
- ECOG Performance Status
- Vital signs, weight and height
- Triplicate 12-lead ECG (2-5 minutes apart)
- Bone marrow aspirate and biopsy
- Tumor biopsy (see Section 7.1.3.4)
- Review of prior and concomitant medications
- CT scan of neck, chest, abdomen, pelvis (and/or MRI for lesions not well-visualized by CT)
- PET scan (in addition to CT scan)
- Clinical laboratory tests for:
 - o Hematology
 - Serum chemistry
 - o TSH
 - Coagulation (PT, PTT, INR)
 - Creatinine Clearance

- Serum pregnancy test (for women of childbearing potential only)
- Hepatitis serologies and HIV
- o Urinalysis
- Research laboratory blood samples:
 - Ibrutinib biomarkers and pharmacodynamics

8.2 Treatment Phase

8.2.1 Ibrutinib Lead-in Day 1 (baseline)

Screening laboratory assessments performed within 48 hours of Ibrutinib Lead-in Day 1 may be used as pre-dose ibrutinib Lead-in Day 1 laboratory assessments and are not required to be repeated.

Pre-dose

- Confirmation of eligibility
- Complete physical exam
- ECOG Performance Status
- Vital signs and weight
- Triplicate 12-lead ECG (2-5 minutes apart)
- Buccal swab
- Clinical laboratory tests for:
 - Hematology
 - Serum chemistry
 - Urine pregnancy test (for women of childbearing potential only)
- Research laboratory blood samples collected pre-dose for:
 - Ibrutinib pharmacokinetics
 - Ibrutinib biomarkers and pharmacodynamics
- Review of AEs and concomitant medications

Dosing

- Dispense ibrutinib and diary card
- In-clinic administration of ibrutinib

Post-dose

- Research laboratory blood samples (see Appendix 2 for collection schedule):
 - Ibrutinib pharmacokinetics
 - Ibrutinib biomarkers and pharmacodynamics
- Triplicate 12-lead ECG (2-5 minutes apart) at approximately 2 hours post ibrutinib dose

• Review of AEs and concomitant medications

8.2.2 Ibrutinib Lead-in Day 2

Pre-dose

- Research laboratory blood samples collected pre-dose for:
 - Ibrutinib pharmacokinetics (24-hour time point from Day 1)
 - Ibrutinib biomarkers and pharmacodynamics (24-hour time point from Day 1)
- Review of AEs and concomitant medications

Dosing

• In-clinic administration of ibrutinib

8.2.3 Ibrutinib Lead-in Day 6 or 7

Pre-dose

- Research laboratory blood samples collected pre-dose for:
 - Ibrutinib pharmacokinetics
 - Ibrutinib biomarkers and pharmacodynamics
- Review of AEs and concomitant medications

Dosing

• In-clinic administration of ibrutinib

Post-dose

- Research laboratory blood samples (See Appendix 2 for collection schedule):
 - Ibrutinib pharmacokinetics
- Review of AEs and concomitant medications

8.2.4 Cycle 1 Day 1 (C1D1)

Pre-dose

- Complete physical exam
- ECOG Performance Status
- Vital signs (within 30 minutes of MEDI4736 infusion start) and weight
- Triplicate 12-lead ECG (2-5 minutes apart) 30-60 minutes prior to MEDI4736 infusion start
- Clinical laboratory tests for:
 - Hematology

- Serum chemistry
- o TSH
- o Urinalysis
- Urine pregnancy test (for women of childbearing potential only)
- Research laboratory blood samples collected pre-dose for:
 - Ibrutinib biomarkers and pharmacodynamics
 - MEDI4736 pharmacokinetics
 - MEDI4736 pharmacodynamics (includes anti-drug antibodies)
- Review of AEs and concomitant medications

Dosing

- In-clinic administration of MEDI4736
- Vital signs every 30 minutes (±5 minutes) during MEDI4736 infusion
- Dispense ibrutinib and diary card
- In-clinic administration of ibrutinib (approximately within 15 minutes of end of MEDI4736 infusion)

Post-dose

- Vital signs at the following timepoints:
 - End of MEDI4736 infusion (+5 minutes)
 - \circ 30 minutes (±5 minutes) post end of MEDI4736 infusion
 - o 60 minutes (±5 minutes) post end of MEDI4736 infusion
 - 2 hours (±15 minutes) post end of MEDI4736 infusion
- Triplicate 12-lead ECG (2-5 minutes apart) within 3 hours after the end of the MEDI4736 infusion
- Research laboratory blood samples (see Appendix 2 for collection schedule):
 - o MEDI4736 pharmacokinetics
 - MEDI4736 pharmacodynamics (to be collected after ibrutinib dose is taken)
- Review of AEs and concomitant medications

8.2.5 Cycle 1 Day 8 (C1D8)

Pre-dose

- Physical exam
- ECOG Performance Status
- Vital signs and weight
- Clinical laboratory tests for:
 - Hematology

- Serum chemistry
- Review of AEs and concomitant medications

8.2.6 Cycle 1 Day 15 (C1D15)

Pre-dose

- Physical exam
- ECOG Performance Status
- Vital signs (within 30 minutes of MEDI4736 infusion start) and weight
- Clinical laboratory tests for:
 - o Hematology
 - o Serum chemistry
- Research laboratory blood samples:
 - Ibrutinib biomarkers and pharmacodynamics
 - MEDI4736 pharmacokinetics
 - o MEDI4736 pharmacodynamics
- Review of AEs and concomitant medications

Dosing

- In-clinic administration of MEDI4736
- Vital signs every 30 minutes (±5 minutes) during MEDI4736 infusion
- In-clinic administration of ibrutinib (approximately within 15 minutes of end of MEDI4736 infusion)

Post-dose

- Vital signs at the following timepoint:
 - End of MEDI4736 infusion (+5 minutes)
- Research laboratory blood samples (see Appendix 2 for collection schedule):
 - o Ibrutinib biomarkers and pharmacodynamics
- Review of AEs and concomitant medications

8.2.7 Cycle 1 Day 22 (C1D22)

- Physical exam
- ECOG Performance Status
- Vital signs and weight
- Clinical laboratory tests for:
 - Hematology

- Serum chemistry
- Review of AEs and concomitant medications

8.2.8 Cycle 2 Day 1 (C2D1)

Pre-dose

- Complete physical exam
- ECOG Performance Status
- Vital signs (within 30 minutes of MEDI4736 infusion start) and weight
- Clinical laboratory tests for:
 - o Hematology
 - Serum chemistry
 - o TSH
 - Urine pregnancy test (for women of childbearing potential only)
- Research laboratory blood samples:
 - Ibrutinib biomarkers and pharmacodynamics
 - MEDI4736 pharmacokinetics
 - MEDI4736 pharmacodynamics (includes anti-drug antibodies)
- Review of AEs and concomitant medications

Dosing

- In-clinic administration of MEDI4736
- Vital signs every 30 minutes (±5 minutes) during MEDI4736 infusion
- Dispense ibrutinib and diary card
- In-clinic administration of ibrutinib (approximately within 15 minutes of end of MEDI4736 infusion)

Post-dose

- Vital signs at the following timepoint:
 - End of MEDI4736 infusion (+5 minutes)
- Research laboratory blood samples (see Appendix 2 for collection schedule):
 - MEDI4736 pharmacokinetics
- Review of AEs and concomitant medications

8.2.9 Cycle 2 Day 15 (C2D15)

Pre-dose

• Physical exam

- ECOG Performance Status
- Vital signs (within 30 minutes of MEDI4736 infusion start) and weight
- Clinical laboratory tests for:
 - Hematology
 - Serum chemistry
- Research laboratory blood samples:
 - Ibrutinib biomarkers and pharmacodynamics
- Review of AEs and concomitant medications

Dosing

- In-clinic administration of MEDI4736
- Vital signs every 30 minutes (±5 minutes) during MEDI4736 infusion
- In-clinic administration of ibrutinib (approximately within 15 minutes of end of MEDI4736 infusion)

Post-dose

- Vital signs at the following timepoint:
 - End of MEDI4736 infusion (+5 minutes)
- Review of AEs and concomitant medications

8.2.10 Cycle 3 Day 1 (C3D1)

Pre-dose

- Complete physical exam
- Response Assessment
- CT scan of neck, chest, abdomen, pelvis (and/or MRI for lesions not well-visualized by CT) can be performed within 7 days prior to C3D1
- ECOG Performance Status
- Vital signs (within 30 minutes of MEDI4736 infusion start) and weight
- Triplicate 12-lead ECG (2-5 minutes apart)
- Clinical laboratory tests for:
 - o Hematology
 - Serum chemistry
 - o TSH
 - Urine pregnancy test (for women of childbearing potential only)
- Research laboratory blood samples:
 - Ibrutinib pharmacokinetics
 - Ibrutinib biomarkers and pharmacodynamics

- o MEDI4736 pharmacokinetics
- MEDI4736 pharmacodynamics (includes anti-drug antibodies)
- Review of AEs and concomitant medications

Dosing

- In-clinic administration of MEDI4736
- Vital signs every 30 minutes (±5 minutes) during MEDI4736 infusion
- Dispense ibrutinib and diary card
- In-clinic administration of ibrutinib (approximately within 15 minutes of end of MEDI4736 infusion)

Post-dose

- Vital signs at the following timepoint:
 - End of MEDI4736 infusion (+5 minutes)
- Research laboratory blood samples (see Appendix 2 for collection schedule):
 - Ibrutinib pharmacokinetics
 - MEDI4736 pharmacokinetics
- Triplicate 12-lead ECG (2-5 minutes apart) at approximately 2 hours post ibrutinib dose
- Review of AEs and concomitant medications

8.2.11 Cycle 3 Day 15 (C3D15)

Pre-dose

- Physical exam
- ECOG Performance Status
- Vital signs (within 30 minutes of MEDI4736 infusion start) and weight
- Clinical laboratory tests for:
 - Hematology
 - Serum chemistry

Note: After Cycle 3, Day 15 hematology and chemistry laboratories can be obtained if clinically indicated.

- Research laboratory blood samples:
 - Ibrutinib biomarkers and pharmacodynamics
- Review of AEs and concomitant medications

Dosing

• In-clinic administration of MEDI4736

- Vital signs every 30 minutes (±5 minutes) during MEDI4736 infusion
- In-clinic administration of ibrutinib (approximately within 15 minutes of end of MEDI4736 infusion)

Post-dose

- Vital signs at the following timepoints:
 - End of MEDI4736 infusion (+5 minutes)
- Review of AEs and concomitant medications

8.2.12 Cycle 4 Day 1 (C4D1)

Pre-dose

- Complete physical exam
- ECOG Performance Status
- Vital signs (within 30 minutes of MEDI4736 infusion start) and weight
- Clinical laboratory tests for:
 - o Hematology
 - Serum chemistry
 - o TSH
 - Urinalysis
 - Urine pregnancy test (for women of childbearing potential only)
- Research laboratory blood samples:
 - Ibrutinib biomarkers and pharmacodynamics
- Review of AEs and concomitant medications

Dosing

- In-clinic administration of MEDI4736
- Vital signs every 30 minutes (±5 minutes) during MEDI4736 infusion
- Dispense ibrutinib and diary card
- In-clinic administration of ibrutinib (approximately within 15 minutes of end of MEDI4736 infusion)

Post-dose

- Vital signs at the following timepoint:
 - End of MEDI4736 infusion (+5 minutes)
- Review of AEs and concomitant medications

8.2.13 Cycle 4 Day 15 (C4D15)

Pre-dose

- Physical exam
- ECOG Performance Status
- Vital signs (within 30 minutes of MEDI4736 infusion start) and weight
- Review of AEs and concomitant medications

Dosing

- In-clinic administration of MEDI4736
- Vital signs every 30 minutes (±5 minutes) during MEDI4736 infusion
- In-clinic administration of ibrutinib (approximately within 15 minutes of end of MEDI4736 infusion)

Post-dose

- Vital signs at the following timepoints:
 - End of MEDI4736 infusion (+5 minutes)
- Review of AEs and concomitant medications

8.2.14 Cycle 5 Day 1 (C5D1)

Pre-dose

- Complete physical exam
- ECOG Performance Status
- Vital signs (within 30 minutes of MEDI4736 infusion start) and weight
- Triplicate 12-lead ECG (2-5 minutes apart)
- Clinical laboratory tests for:
 - Hematology
 - Serum chemistry
 - o TSH
 - Urine pregnancy test (for women of childbearing potential only)
- Research laboratory blood samples:
 - Ibrutinib biomarkers and pharmacodynamics
- Review of AEs and concomitant medications

Dosing

- In-clinic administration of MEDI4736
- Vital signs every 30 minutes (±5 minutes) during MEDI4736 infusion
- Dispense ibrutinib and diary card

• In-clinic administration of ibrutinib (approximately within 15 minutes of end of MEDI4736 infusion)

Post-dose

- Vital signs at the following timepoints:
 - End of MEDI4736 infusion (+5 minutes)
- Triplicate 12-lead ECG (2-5 minutes apart) 30-60 minutes within 3 hours after the end of MEDI4736 infusion
- Review of AEs and concomitant medications

8.2.15 Cycle 5 Day 15 (C5D15)

Pre-dose

- Physical exam
- ECOG Performance Status
- Vital signs (within 30 minutes of MEDI4736 infusion start) and weight
- Review of AEs and concomitant medications

Dosing

- In-clinic administration of MEDI4736
- Vital signs every 30 minutes (±5 minutes) during MEDI4736 infusion
- In-clinic administration of ibrutinib (approximately within 15 minutes of end of MEDI4736 infusion)

Post-dose

- Vital signs at the following timepoint:
 - End of MEDI4736 infusion (+5 minutes)
- Review of AEs and concomitant medications

8.2.16 Cycle 6 Day 1 (C6D1)

Pre-dose

- Complete physical exam
- Response Assessment
- CT scan of neck, chest, abdomen, pelvis (and/or MRI for lesions not well-visualized by CT) can be performed within 7 days prior to C6D1
- ECOG Performance Status
- Vital signs (within 30 minutes of MEDI4736 infusion start) and weight
- Clinical laboratory tests for:
 - Hematology

- Serum chemistry
- o TSH
- Urine pregnancy test (for women of childbearing potential only)
- Research laboratory blood samples:
 - Ibrutinib biomarkers and pharmacodynamics
 - MEDI4736 pharmacokinetics
 - MEDI4736 pharmacodynamics (includes anti-drug antibodies)
- Review of AEs and concomitant medications

Dosing

- In-clinic administration of MEDI4736
- Vital signs every 30 minutes (±5 minutes) during MEDI4736 infusion
- Dispense ibrutinib and diary card
- In-clinic administration of ibrutinib (approximately within 15 minutes of end of MEDI4736 infusion)

Post-dose

- Vital signs at the following timepoint:
 - End of MEDI4736 infusion (+5 minutes)
- Review of AEs and concomitant medications
- Research laboratory blood samples (see Appendix 2 for collection schedule):
 - o MEDI4736 pharmacokinetics

8.2.17 Cycle 6 Day 15 (C6D15)

Pre-dose

- Physical exam
- ECOG Performance Status
- Vital signs (within 30 minutes of MEDI4736 infusion start) and weight
- Review of AEs and concomitant medications

Dosing

- In-clinic administration of MEDI4736
- Vital signs every 30 minutes (±5 minutes) during MEDI4736 infusion
- In-clinic administration of ibrutinib (approximately within 15 minutes of end of MEDI4736 infusion)

Post-dose

• Vital signs at the following timepoint:

- End of MEDI4736 infusion (+5 minutes)
- Review of AEs and concomitant medications

8.2.18 Day 1 of Each Subsequent Cycle

Subjects will continue to come in on Day 1 of each cycle for the first 12 months. After this time, subjects will come in on Day 1 of every third cycle. The following procedures will be performed unless otherwise specified.

Pre-dose

- Complete physical exam
- Response Assessment
- CT scan of neck, chest, abdomen, pelvis (and/or MRI for lesions not well-visualized by CT) should be performed every 3 cycles (Cycle 9, Cycle 12 and every 6 cycles thereafter)
- ECOG Performance Status
- Vital signs (within 30 minutes of MEDI4736 infusion start) and weight
- Clinical laboratory tests for:
 - Hematology (every cycle through Cycle 12, then at every 3 cycles thereafter)
 - Serum chemistry (every cycle through Cycle 12, then at every 3 cycles thereafter)
 - TSH (every cycle through Cycle 12, then at every 3 cycles thereafter)
 - Urinalysis (on Cycle 7 and Cycle 10)
 - Urine pregnancy test (for women of childbearing potential only) (every cycle through Cycle 12, then at every 3 cycles thereafter)
- Research laboratory blood samples (on Cycle 7 and every 2 cycles thereafter, until CR achieved, then every 3 cycles thereafter):
 - Ibrutinib biomarkers and pharmacodynamics
- Research laboratory blood samples (on Cycle 9 and every 3 cycles thereafter):
 - Ibrutinib biomarkers and pharmacodynamics
 - MEDI4736 pharmacokinetics
 - MEDI4736 pharmacodynamics (includes anti-drug antibodies)
- Review of AEs and concomitant medications

Dosing

- In-clinic administration of MEDI4736
- Vital signs every 30 minutes (±5 minutes) during MEDI4736 infusion
- Dispense ibrutinib and diary card (every cycle through Cycle 12, then at every 3 cycles thereafter)

• In-clinic administration of ibrutinib (approximately within 15 minutes of end of MEDI4736 infusion)

Post-dose

- Vital signs at the following timepoint:
 - End of MEDI4736 infusion (+5 minutes)
- Research laboratory blood samples (on Cycle 9 and every 3 cycles thereafter; see Appendix 2 for collection schedule):
 - MEDI4736 pharmacokinetics
- Review of AEs and concomitant medications

8.2.19 Day 15 of Each Subsequent Cycle

The Day 15 visits can be discontinued at the end of treatment with MEDI4736.

Pre-dose

- Physical exam
- ECOG Performance Status
- Vital signs (within 30 minutes of MEDI4736 infusion start) and weight
- Review of AEs and concomitant medications

Dosing

- In-clinic administration of MEDI4736
- Vital signs every 30 minutes (± 5 minutes) during MEDI4736 infusion
- In-clinic administration of ibrutinib (approximately within 15 minutes of end of MEDI4736 infusion)

Post-dose

- Vital signs at the following timepoint:
 - End of MEDI4736 infusion (+5 minutes)
- Review of AEs and concomitant medications

8.2.20 **Response Evaluations**

Response evaluations will be performed per the schedule outlined in Appendix 1. Imaging should be performed in the 7 days prior to the first dose of the next cycle. The following procedures will be performed in conjunction with standard visits as follows:

- CT scan of neck, chest, abdomen, pelvis (and/or MRI for lesions not well-visualized by CT)
- Response Assessment

- To be completed to confirm CR:
 - PET scan (in addition to CT scan)
 - Bone marrow aspirate and biopsy
 - Ibrutinib biomarkers and pharmacodynamics (unless already obtained within the last 7 days)

8.2.21 Treatment Termination (Optional Visit)

At the time of disease progression, an optional Treatment Termination visit may occur. The purpose of this visit is to allow an opportunity to collect biomarker samples and subject information at the time of disease progression prior to treatment discontinuation. If possible, the visit should be performed within 4 to 24 hours after the subject's previous dose. An optional tumor tissue biopsy may be collected at disease progression. In conjunction with this optional visit, CT or MRI and/or PET scans may be done per Investigator discretion to assess for PD.

The following procedures will be performed:

- Physical exam
- ECOG Performance Status
- Vital signs and weight
- Clinical laboratory tests for:
 - Hematology
 - Serum chemistry
- CT scan of neck, chest, abdomen, pelvis (if needed per Investigator discretion)
- PET scan (if needed per Investigator discretion)
- Response Assessment
- Tumor biopsy (if feasible) (see Section 7.1.3.4)
- Research laboratory blood samples:
 - Ibrutinib biomarkers and pharmacodynamics
 - MEDI4736 pharmacokinetics
 - o MEDI4736 pharmacodynamics

8.3 Follow-up Phase

Once a subject has completed the Treatment Phase, they will enter the Post-treatment Phase. Subjects that withdraw from treatment for reasons other than progressive disease will participate in ongoing response follow-up discussed in Section 8.3.3.

8.3.1 End-of-Treatment Visit for Ibrutinib

An End-of-Treatment visit should occur 30 days (\pm 7 days) after the last dose of ibrutinib or prior to the start of a new anticancer treatment. This visit may occur as a standard study visit if the

subject continues treatment with MEDI4736 alone. An optional tumor tissue biopsy may be collected if treatment was discontinued due to disease progression. If the subject starts a new anticancer treatment less than 7 days after the Treatment Termination visit, only those procedures not conducted at the Treatment Termination visit should be performed at the End-of-Treatment visit.

Subjects who withdraw consent to treatment may still participate in End-of-Treatment visit. The following procedures will be performed at the End-of-Treatment visit:

- Complete physical exam
- ECOG Performance Status
- Vital signs and weight
- Triplicate 12-lead ECG (2-5 minutes apart)
- Clinical laboratory tests for:
 - Hematology
 - Serum chemistry
- Research laboratory blood samples collected:
 - Ibrutinib biomarkers and pharmacodynamics (unless already obtained within the last 7 days)
- Review of AEs and concomitant medications

8.3.2 End-of-Treatment Visit for MEDI4736

An End-of-Treatment visit should occur 90 days (±7 days) after the last dose of MEDI4736 or prior to the start of a new anticancer treatment. This visit may occur as a standard Day 1 cycle study visit if the subject continues treatment with ibrutinib alone. Subjects who withdraw consent to treatment may still participate in the End-of-Treatment visit. The following procedures will be performed:

- Complete physical exam
- ECOG Performance Status
- Vital signs and weight
- Clinical laboratory tests for:
 - Hematology
 - o Serum chemistry
 - o TSH
 - o Urinalysis
 - Review of AEs and concomitant medications
- Research laboratory blood samples:
 - MEDI4736 pharmacokinetics

• MEDI4736 pharmacodynamics (includes anti-drug antibodies)

8.3.3 Response Follow-up

Subjects who discontinue the study treatments (both ibrutinib and MEDI4736) for reasons other than progressive disease will be followed every 12 weeks (\pm 7 days) until progressive disease or death, up to 3 years after the first dose of the last subject enrolled. The following procedures will be performed:

- Physical examination
- CT scan of neck, chest, abdomen, pelvis (and/or MRI for lesions not well-visualized by CT) at the end of Cycle 2 (within 7 days prior to starting Cycle 3) and then again every third cycle (within 7 days prior to starting the next cycle)
- PET scan (if needed to confirm PD per Investigator discretion)
- Response assessment

8.3.4 Survival Follow-up

Once subjects progress or start use of alternative anticancer therapy (for subjects who have not withdrawn consent), they will be contacted approximately every 12 weeks (\pm 7 days) from the last dose by clinic visit or telephone to assess survival and the use of alternative anticancer therapy, up to 3 years after the last dose of the last subject enrolled. Subjects will be contacted until death, subject withdrawal, lost to follow-up, or study termination by the Sponsor, whichever occurs first.

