12.2	Institutional Review Board (IRB), Research Ethics Board (REB) and Independent	
	Ethics Committee (IEC) Approval.	117
12.3	Informed Consent	117
12.4	Quality Control and Quality Assurance	118
12.5	Protected Subject Health Information Authorization	118
12.6	Study Files and Record Retention.	18
12.7	Case Report Forms and Record Maintenance	119
12.8	Investigational Study Drug Accountability	120
12.9	Study Monitoring/Audit Requirements	120
12.10	Investigator Responsibilities	121
12.11	Sponsor Responsibilities	121
12.12	Financial Disclosure	122
12.13	Liability and Clinical Trial Insurance	122
12.14	Protocol Amendments	122
12.15	Publication of Study Results	23
12.16	Study Discontinuation	23
13. R	EFERENCES	124
14. A	PPENDICES	129

LIST OF IN-TEXT TABLES

Table 1.	Overview of Ongoing Clinical Studies of MEDI4736 in Which Subjects Have	
	Been Treated	33
Table 2.	Phase 1b Dosing Levels	43
Table 3.	Ibrutinib Dose Modifications	57
Table 4.	Dose Modification and Toxicity Management Guidelines for Immune-mediate	ed,
	Infusion Related, and Non Immune-mediated MEDI4736-related Adverse	
	Reactions	59

LIST OF APPENDICES

Appendix 1.	Schedule of Assessments for Phase 1b and Phase 2	130
Appendix 2.	Schedule of Assessments for Pharmacokinetics, Pharmacodynamics, and	
	Biomarkers: Phase 1b and Phase 2	132
Appendix 3.	ECOG Performance Status Scores	134
Appendix 4.	Inhibitors and Inducers of CYP3A	135
Appendix 5.	Revised Criteria for Response Assessment of Malignant Lymphoma	
	(Cheson 2014)	136
Appendix 6.	New York Heart Association (NYHA) Functional Classification	139
Appendix 7.	Contraception Requirements for MEDI4736	140

SYNOPSIS

Study Title:	A Multi-Center Open-Label Study of the Bruton's Tyrosine Kinase (BTK) Inhibitor Ibrutinib, in Combination with MEDI4736, in Subjects with Relapsed or Refractory Lymphomas
Protocol Number:	РСҮС-1136-СА
Study Phase:	1b/2
Study Duration:	Estimated to be approximately 3 years
Number of Subjects:	Approximately 109 subjects will be enrolled throughout the study (up to 36 subjects in Phase 1b and approximately 73 subjects in Phase 2)
Investigational Product and Reference Therapy:	Ibrutinib will be supplied as 140 mg hard gelatin capsules for oral (PO) administration. MEDI4736 will be supplied in glass vials containing 500 mg of liquid solution at a concentration of 50 mg/mL for intravenous (IV) administration.
Objectives:	Phase 1b: Primary Objectives:

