Dosing of ibrutinib in combination with MEDI4736 will continue for a total of 12 cycles of therapy if the subject is deriving clinical benefit (CR, PR, or SD) and the subject is not experiencing unacceptable toxicity. After 12 cycles, dosing of ibrutinib alone will continue as long as clinical benefit is seen without safety concerns or disease progression.

Response evaluations will occur on Cycle 3 Day 1, Cycle 6 Day 1, Cycle 9 Day 1, Cycle 12 Day 1, and every 6 cycles thereafter. Assessment will follow the Revised Criteria for Response Assessment of Malignant Lymphoma (Cheson 2014).

In order to accommodate the potential for immune flare (pseudoprogression), treatment with MEDI4736 and ibrutinib may continue between the initial assessment of progression and confirmation for progression. Subjects with presumed PD who, in the Investigator's opinion, continue to receive clinical benefit from their treatment may continue to receive MEDI4736 and ibrutinib as dictated in the protocol after consultation with the Sponsor and at the Investigator's discretion (see Section 12.11). In the absence of clinically significant deterioration, a CT scan or biopsy may be performed at least 4 weeks later to confirm PD. If PD is confirmed at the later time point, PD should be assigned to the prior time point at which PD criteria were also met. MEDI4736 and ibrutinib should be discontinued if there is confirmed PD per Revised Criteria for Response Assessment of Malignant Lymphoma (Cheson 2014) or other clinical data suggest clear evidence of progression.

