5.5 Study Treatment

All eligible subjects will be treated with ibrutinib PO and MEDI4736 IV in 28-day cycles. Prior to the first cycle, ibrutinib will be given daily for 7 days in the ibrutinib lead-in period prior to starting MEDI4736. On infusion days where pharmacokinetic, pharmacodynamic, or biomarker samples are drawn post-dose, MEDI4736 IV should be given first, with administration of ibrutinib as soon as possible after the end of infusion.

Missed doses of ibrutinib and MEDI4736 will not be made up. Dose modification of MEDI4736 will not be permitted.

Dosing of ibrutinib will continue up to 3 years as long as the subject is deriving clinical benefit (CR, PR, or SD) and the subject is not experiencing unacceptable toxicity. Dosing of MEDI4736 will continue for a total of 12 cycles of therapy if clinical benefit is seen without safety concerns. Toxicity may result in discontinuation or hold of one study drug while the other may continue to be dosed. Depending on the suspected relatedness to either agent (or both), the Investigator may perform dose modification and/or dose delays as per Section 5.6.1.4 and/or Section 5.6.2.5 at his or her clinical discretion. Re-treatment with MEDI4736 will not be allowed following completion of 12 cycles of treatment, regardless of any dose delays, missed doses, or following permanent discontinuation for any reason.

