9.2 Withdrawal from Study Treatment

Study treatment will be discontinued in the event of any of the following events:

- Progressive disease
- Unacceptable toxicity: an AE that prevents further administration of ibrutinib and MEDI4736 (including a DLT)
- Withdrawal of consent for treatment by subject
- Investigator decision (such as chronic noncompliance, significant protocol deviation, or best interest of the subject)
- Study termination by Sponsor
- Subject becomes pregnant

All subjects, regardless of reason for discontinuation of study treatment will undergo an End-of-Treatment Visit and be followed for progression and survival.

The Investigator should notify the Sponsor within 24 hours if a subject discontinues ibrutinib and/or MEDI4736 treatment due to disease progression or a DLT and should provide redacted documentation of disease progression for review by the Sponsor's Medical Monitor. If a subject shows signs of disease progression on physical examination or laboratory assessment, the subject may continue study treatment until disease progression is confirmed. These subjects should stay in the study to be followed for survival.

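### Response and survival follow-up close on different dates, so late overall survival (OS) is at risk of informative censoring among off-treatment subjects; Sections 8.3.3, 8.3.4, 9.2 and Appendix 1 need one common rule

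*Protocol*

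**What the plan says.** **Response follow-up (Protocol 8.3.3).** Subjects who stop both drugs for reasons other than progression are seen every 12 weeks until progression or death, "up to 3 years after the first dose of the last subject enrolled".

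**Survival follow-up (Protocol 8.3.4).** Contact begins "Once subjects progress or start use of alternative anticancer therapy" and continues about every 12 weeks, "up to 3 years after the last dose of the last subject enrolled". It can end sooner, because subjects are contacted "until death, subject withdrawal, lost to follow-up, or study termination by the Sponsor, whichever occurs first". Appendix 1 labels this column as post-PD.

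**All subjects (Protocol 9.2).** Whatever the reason for stopping treatment, subjects will "be followed for progression and survival". No schedule or end date is attached.

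**Length of ibrutinib dosing.** Section 5.5 says "Dosing of ibrutinib will continue up to 3 years as long as the subject is deriving clinical benefit". Section 3.1.2 says that after 12 cycles "dosing of ibrutinib alone will continue as long as clinical benefit is seen", with no time limit.

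**OS analysis.** OS is a Phase 2 secondary endpoint. Protocol 10.6.2.2 leaves its censoring rules to the SAP. SAP Table 1 counts all deaths in the treated population and asks for a Kaplan-Meier curve, but gives no censoring rule. SAP 3.1 defines time on study as OS with censoring reversed.

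**Study duration (Protocol Synopsis).** "Estimated to be approximately 3 years", with neither the start nor the end event defined.

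**The concern.** Kaplan-Meier assumes that subjects censored at a given time have the same later risk of death as those still followed. Two end dates that depend on progression status break this. Once response follow-up closes, off-treatment subjects who are progression-free drop out of scheduled contact, while those who have progressed or been re-treated stay in it. The remaining risk set has the worse outlook, so the late part of the curve falls too steeply. Median time on study, which uses the same censoring dates reversed, inherits the problem.

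The SAP has no OS censoring rule that would neutralise this. A site working from the schedule in Appendix 1 would also have no prompt to carry out the broader promise in Section 9.2.

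**Working it through.** **1. The two end dates.** Let A be the accrual time (not given in the documents) and T the last enrolled subject's treatment time. Measured from the first subject's first dose:

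- response cap = A + 3 years
- survival cap = A + T + 3 years
- gap = T

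| | A = 0 | A = 1 | A = 2 |
|---|---|---|---|
| Response cap (years) | 3.0 | 4.0 | 5.0 |
| Survival cap, T = 2 months | 3.17 | 4.17 | 5.17 |
| Survival cap, T = 12 cycles plus lead-in, (12 × 28 + 7)/365.25 = 0.94 years | 3.94 | 4.94 | 5.94 |
| Survival cap, T = 3 years (Section 5.5 limit) | 6.0 | 7.0 | 8.0 |

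The gap can be a couple of months or as long as 3 years under Section 5.5. Under Section 3.1.2 it has no stated limit. If the last subject took ibrutinib for the full 3 years, response follow-up would close as dosing stopped, and that subject would have no off-treatment response follow-up.

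**2. When bias can start.** The response cap runs from the last subject's first dose, so nobody reaches it before 36 months from their own first dose. Until then progression-free subjects are seen on treatment or every 12 weeks, and their deaths are captured. The bias is therefore zero through 36 months.

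**3. Size in the limiting case of zero accrual.** The model takes one figure from the documents: median PFS of 13.4 months, from the earlier ibrutinib study in FL (Protocol 1.3). The rest is assumed: exponential times, every death follows progression, median post-progression survival m of 12, 24 or 36 months, a 24-month gap, and all progression-free subjects off drug.

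With a = ln 2/13.4 and b = ln 2/m:

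- progression-free at 36 months = exp(−36a) = 15.5%
- true OS: S(t) = exp(−at) + [a/(a − b)] × [exp(−bt) − exp(−at)]
- at zero accrual, all progression-free subjects are censored at 36 months and only progressed subjects remain, so Kaplan-Meier at 60 months = S(36) × exp(−24b)

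| m (months) | S(36) | exp(−24b) | Kaplan-Meier at 60 | True S(60) | Bias (points, from unrounded values) |
|---|---|---|---|---|---|
| 12 | 41.5% | 0.25 | 10.4% | 16.2% | −5.8 |
| 24 | 60.4% | 0.50 | 30.2% | 34.4% | −4.1 |
| 36 | 70.4% | 0.63 | 44.4% | 47.5% | −3.1 |

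**4. With accrual.** A subject enrolled earlier reaches the response cap later in their own time. Simulating the same model with uniform accrual gives this bias at 60 months, to within about 0.1 point:

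| Accrual | m = 12 | m = 24 | m = 36 |
|---|---|---|---|
| 12 months | −4.2 | −2.8 | −2.1 |
| 24 months | −2.5 | −1.7 | −1.3 |

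With a 2-month gap and 24 months' accrual, the bias is no more than 1.0 point.

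**5. Sensitivity to long-term non-progressors.** A second assumed model keeps the PFS median, sets m to 2 years, and adds 2% per year death without progression. At years 5 to 6, with 12 months' accrual and a 3-year gap, the bias is about −2.5 points if nobody is a durable non-progressor. It is about −8 to −16 points if 20–30% never progress. The documents give no such fraction, so the larger range shows only what the result is sensitive to.

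**6. The stated duration.** The full response window fits into 3 years only if A = 0. The full survival window never fits when T > 0. Three years does match the earliest FL primary analysis, 12 months after last enrolment, if accrual takes about 2 years (2 + 1 = 3). That accrual time is an assumption.

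**The case against.** **Broader follow-up is promised elsewhere.** A reader might infer that late OS is, by design, observed only in subjects with a poorer prognosis. The documents do not settle that. Section 9.2 promises survival follow-up for all. Section 7.1.1.4 collects later anticancer therapy after any treatment discontinuation until death, withdrawal of full consent, loss to follow-up or study termination, with no progression condition and no 3-year cap. Section 3.1.1 promises OS follow-up for Phase 1b subjects not treated at the RP2D. This stands: the fault is an internal conflict, and the bias arises if the schedule is what sites follow.

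**Only off-treatment subjects are affected.** Section 8.3.3 covers subjects off both drugs. Under the open-ended wording of Section 3.1.2, progression-free subjects still on ibrutinib stay under observation. This also stands. Assuming that all of them are off drug gives the larger effect on this point.

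**The size is easy to overstate.** Starting from the zero-accrual table, a reader might infer a bias of 3 to 6 points. That requires everyone to start on the same day. Any realistic accrual shrinks it, and so does a short gap. For scale, the binomial standard error of OS near 34% with 39 FL subjects is √(0.34 × 0.66/39) = 7.6 points, even without censoring.

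**The 3-year duration.** A reader might infer that it contradicts both windows. It is an approximate estimate without defined endpoints, set against two ceilings, and the Sponsor may stop earlier (8.3.4 and 12.16). It needs clarifying, but a contradiction is not shown.

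**Little depends on late OS.** It is secondary and single-arm. The only stated timing for the main analysis is a minimum of 12 months (FL) or 9 months (DLBCL) after last enrolment, and no 48- or 60-month OS analysis is specified. That limits the consequence. It does not remove the mismatch or fill the gap in the SAP.

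**Conclusion.** The point holds as a conflict between Sections 8.3.3, 8.3.4 and Appendix 1 on one side and Section 9.2 on the other. If the schedule is followed, off-treatment subjects have survival contact between the two caps only when they have progressed or started new therapy, and late Kaplan-Meier OS is biased downward.

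The effect is bounded:

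- It is zero within 3 years of first dose.
- At 60 months it is about 2 to 4 points with 12 months' accrual and about 1 to 2.5 points with 24 months'. It is smaller with a short gap.
- Those figures rest on median PFS of 13.4 months from the protocol, and on assumed post-progression medians of 12 to 36 months, a 24-month gap, and all progression-free subjects off drug.
- ORR is unaffected, and so is an analysis at the 9- to 12-month minimum.

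The direction is known and the remedy is cheap, so it is worth correcting even though the primary conclusion does not depend on it.

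**What to change.** Either of these removes the differential censoring:

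1. **Protocol amendment.** Give survival status one anchor and one end date for all treated subjects, progressed or not. Move those still progression-free when response follow-up closes to the 12-weekly survival contact. The cost is amendment wording and some telephone contacts.
2. **SAP rule.** Censor OS for everyone at the earlier cut-off, 3 years after the last subject's first dose. There is no field cost. The downside is losing a few late OS events.

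Under either option, write into the SAP the OS censoring rule that Protocol 10.6.2.2 defers to it. Reconcile Sections 8.3.3, 8.3.4, 9.2 and Appendix 1. The Sponsor should also reconcile the dosing-duration statements in Sections 3.1.2 and 5.5, because they determine how long the gap can be. Finally, state which start and end events the approximate 3-year study duration covers.
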